**Table 2: Adequate Organ Function Laboratory Values:**

	System	Laboratory Value
	Hematological:	
	Absolute Neutrophil Count ANC	$\geq$ 1,500/uL
	Platelets	$\geq$ 100,000/uL
	Hemoglobin	$\geq$ 9 g/dL
	Renal	
	Serum Creatinine OR measured calculated creatinine clearance (GFR may also be used in place of creatinine or CrCl)	$\leq$ 1.5 upper limit of normal (ULN) OR $\geq$ 60 mL/min for subject with creatinine levels $\geq$ 1.5 X institutional ULN
	Hepatic	

	Serum total bilirubin	$\leq 1.5 \times \text{ULN}$ OR Direct bilirubin $\leq \text{ULN}$ for subjects with total bilirubin $\geq 1.5 \times \text{ULN}$
	AST or ALT	$\leq 2.5 \times \text{ULN}$ OR $\leq 5 \times \text{ULN}$ for subjects with liver metastases
	Coagulation	
	International Normalized Ratio (INR) or Prothrombin Time (PT) Activated Partial Thromboplastin Time (aPTT)	$\leq 1.5 \times \text{ULN}$ If on active anticoagulants prior to study treatment, levels must be within standard therapeutic ranges per investigator.

**5.1.7** \_\_\_\_\_ Subjects with a history of known central nervous system (CNS) metastases must have documentation of stable or improved brain imaging for at least 2 weeks after completion of definitive treatment. Definitive treatment may include surgical resection, whole brain irradiation, and/or stereotactic radiation therapy.

**5.1.8** \_\_\_\_\_ Female subject of childbearing potential should have a negative urine or serum pregnancy within 72 hours prior to receiving the first dose of study medication. If the urine test is positive or cannot be confirmed as negative, a serum pregnancy test will be required.

**5.1.9** \_\_\_\_\_ Female subjects of childbearing potential should be willing to use 2 methods of birth control or be surgically sterile, or abstain from heterosexual activity for the course of the study through 120 days after the last dose of study medication. Subjects of childbearing potential are those who have not been surgically sterilized or have not been free from menses for > 1 year (according to Section 8.4.2).

**5.1.10** \_\_\_\_\_ Male subjects should agree to use an adequate method of contraception starting with the first dose of study therapy through 120 days after the last dose of study therapy (according to Section 8.4.2).

**5.1.11** \_\_\_\_\_ Must have recovered from adverse effects of any prior surgery, radiotherapy or other antineoplastic therapy.

**5.1.12** \_\_\_\_\_ Last dose of any antineoplastic therapy  $\geq 2$  weeks (including chemotherapy, small molecule inhibitors, radiation, and/or other investigational anticancer agents). Patients receiving hormone manipulation (e.g. SERMs, aromatase inhibitors, LHRH agonist, etc.) for reasons other than treatment of metastatic breast cancer may continue this treatment at the discretion of the investigator.

**5.1.13** \_\_\_\_\_ Able to provide informed consent and willing to sign an approved consent form that conforms to federal and institutional guidelines.

## **5.2 Exclusion Criteria**

### **Yes/No (Response of “yes” = patient ineligible)**

**5.2.1**  Is currently participating and receiving study therapy or has participated in a study of an investigational agent and received study therapy or used an investigational device within 2 weeks of the first dose of treatment.

**5.2.2**  Has a diagnosis of immunodeficiency or receiving steroid therapy of any other form of immunosuppressive therapy within 7 days prior to first dose of trial treatment. Subjects who receive daily steroid replacement therapy serve as an exception to this rule. Daily prednisone at doses of 5 to 7.5 mg (or hydrocortisone equivalent doses) is an example of replacement therapy.

**5.2.3**  Has a known history of active TB (Bacillus Tuberculosis).

**5.2.4**  Hypersensitivity to pembrolizumab or any of its excipients.

**5.2.5**  Has had a prior anti-cancer monoclonal antibody (mAb) within 4 weeks prior to study Day 1 or who has not recovered (i.e.,  $\leq$  Grade 1 or at baseline) from adverse events due to agents administered more than 4 weeks earlier.

**5.2.6**  Has had prior chemotherapy, targeted small molecule therapy, or radiation therapy within 2 weeks prior to study Day 1 or who has not recovered (i.e.,  $\leq$  Grade 1 or at baseline) from adverse events due to a previously administered agent. Note: Subjects with  $\leq$  Grade 2 neuropathy are an exception to this criterion and may qualify for the study. Note: If subject received major surgery, they must have recovered adequately from the toxicity and/or complications from the intervention prior to starting therapy. Patients receiving hormone manipulation (e.g. tamoxifen, aromatase inhibitors, LHRH agonist, etc.) for reasons other than treatment of metastatic breast cancer may continue this treatment at the discretion of the investigator.

**5.2.7**  Has a known additional malignancy that is progressing or requires active treatment. Exceptions include basal cell carcinoma of the skin or squamous cell carcinoma of the skin that has undergone potentially curative therapy or in situ cervical cancer. Patients on long-term adjuvant therapy with no evidence of disease are not excluded if felt appropriate by investigator.

**5.2.8**  Has known active central nervous system (CNS) metastases and/or carcinomatous meningitis. Subjects with previously treated brain metastases may participate provided they are stable (without evidence of progression by imaging for at least 2 weeks prior to the first dose of trial treatment and any neurologic symptoms have returned to baseline), have no evidence of new or enlarging brain metastases, and are not using steroids for at least 7 days prior to trial treatment. This exception does not include carcinomatous meningitis which is excluded regardless of clinical stability.

**5.2.9**  Has active autoimmune disease that has required systemic treatment in the past 2 years (i.e. with use of disease modifying agents, Replacement therapy (e.g. thyroxine, insulin, or physiologic corticosteroid replacement therapy for adrenal or pituitary insufficiency, etc.) is not considered a form of systemic treatment.

**5.2.10**  Has known history of (non-infectious) pneumonitis that required steroids or has current pneumonitis.

**5.2.11**  Has an active infection requiring systemic therapy.

**5.2.12**  Has a history or current evidence of any condition, therapy, or laboratory abnormality that might confound the results of the trial, interfere with the subject's participation for the full duration of the trial, or is not in the best interest of the subject to participate, in the opinion of the treating investigator.

**5.2.13**  Has known psychiatric or substance abuse disorders that would interfere with cooperation with the requirements of the trial.

**5.2.14**  Is pregnant or breastfeeding, or expecting to conceive or father children within the projected duration of the trial, starting with the pre-screening or screening visit through 120 days after the last dose of trial treatment.

**5.2.15**  Has received prior therapy with an anti-PD-1, anti-PD-L1, or anti-PD-L2 agent.

**5.2.16**  Has a known history of Human Immunodeficiency Virus (HIV) (HIV 1/2 antibodies).

**5.2.17**  Has known active Hepatitis B (e.g., HBsAg reactive) or Hepatitis C (e.g., HCV RNA [qualitative] is detected).

**5.2.18**  Has received a live vaccine within 30 days of planned start of study therapy.  
Note: Seasonal influenza vaccines for injection are generally inactivated flu vaccines and are allowed; however intranasal influenza vaccines (e.g., Flu-Mist®) are live attenuated vaccines, and are not allowed.

**Time**

## **6 STRATIFICATION FACTORS**

Not applicable – all patients will be enrolled on one arm

## **7 TREATMENT PLAN**

Treatment should be administered on Day 1 of each cycle after all procedures and assessments have been completed as detailed on the Study Calendar (Section 9). Trial treatment may be administered up to 3 days before or after the scheduled Day 1 of each cycle due to administrative reasons.

All trial treatments will be administered on an outpatient basis.

### **7.1 Administration Schedule**

Pembrolizumab 200 mg will be administered as a 30 minute IV infusion every 3 weeks. Sites should make every effort to target infusion timing to be as close to 30 minutes as possible. However, given the variability of infusion pumps from site to site, a window of -5 minutes and +10 minutes is permitted (i.e., infusion time is 30 minutes: -5 min/+10 min).

### **7.2 Pembrolizumab (MK-3475) Treatment**

#### **7.2.1 How Supplied, Stored, Packaged and Labeled**

The investigator shall take responsibility for and shall take all steps to maintain appropriate records and ensure appropriate supply, storage, handling, distribution and usage of investigational product in accordance with the protocol and any applicable laws and regulations.

Clinical Supplies will be provided by Merck as summarized in the table below.

Product Name & Potency	Dosage Form
Pembrolizumab 50 mg	Lyophilized Powder for Injection
Pembrolizumab 100 mg/ 4mL	Solution for Injection

#### **7.2.2 Packaging and Labeling Information**

Clinical supplies will be affixed with a clinical label in accordance with regulatory requirements.

#### **7.2.3 Clinical Supplies Disclosure**

This trial is open-label; therefore, the subject, the trial site personnel, the Sponsor and/or designee are not blinded to treatment. Drug identity (name, strength) is included in the label text; random code/disclosure envelopes or lists are not provided.

#### **7.2.4 Storage and Handling Requirements**

Clinical supplies must be stored in a secure, limited-access location under the storage conditions specified on the label.

Receipt and dispensing of trial medication must be recorded by an authorized person at the trial site.

Clinical supplies may not be used for any purpose other than that stated in the protocol.

### **7.2.5 Returns and Reconciliation**

The investigator is responsible for keeping accurate records of the clinical supplies received from Merck or designee, the amount dispensed to and returned by the subjects and the amount remaining at the conclusion of the trial.

Upon completion or termination of the study, all unused and/or partially used investigational product will be destroyed at the site per institutional policy. It is the Investigator's responsibility to arrange for disposal of all empty containers, provided that procedures for proper disposal have been established according to applicable federal, state, local and institutional guidelines and procedures, and provided that appropriate records of disposal are kept.

### **7.2.6 Preparation and Administration**

**Pembrolizumab (MK-3475) Solution for Infusion, 100 mg/ 4 mL vial:** pembrolizumab (MK-3475) Solution for Infusion vials should be stored at refrigerated conditions (2 – 8 °C) and protected from light.

**Note:** vials should be stored in the original box to ensure the drug product is protected from light.

Pembrolizumab (MK-3475) infusion solutions should be prepared in **0.9% Sodium Chloride Injection, USP** (normal saline) or regional equivalent or **5% Dextrose Injection, USP** (5% dextrose) or regional equivalent and the final concentration of pembrolizumab (MK-3475) in the infusion solutions should be between 1 mg/mL and 10 mg/mL.

Please note, the preferred diluent is 0.9% Sodium Chloride and 5% dextrose is only permissible if normal saline is not available.

Local guidelines should be followed for collection of diluent information such as manufacturer, lot and expiry. When the diluent is provided by Merck, the drug accountability log should be used for collection of diluent information.

**Pembrolizumab (MK-3475) SHOULD NOT BE MIXED WITH OTHER DILUENTS.**

Pembrolizumab (MK-3475) solutions may be stored at room temperature for a cumulative time of up to 4 hours. This includes room temperature storage of admixture solutions in the IV bags and the duration of infusion

In addition, IV bags may be stored under refrigeration at 2 °C to 8 °C (36 °F to 46 °F) for up to 20 hours. If refrigerated, allow the IV bags to come to room temperature prior to use.

Parenteral drug products should be inspected visually for particulate matter and discoloration prior to administration. Discard the drug product vial if extraneous particulate matter other than translucent to white proteinaceous particles is observed.

Sites should follow their SOPs for drug transport and delivery, with all possible effort to minimize agitation of the drug product between the pharmacy and the clinic

**DO NOT USE PEMBROLIZUMAB (MK-3475) IF DISCOLORATION IS OBSERVED.**

**DO NOT SHAKE OR FREEZE THE VIAL(S).**

**DO NOT ADMINISTER THE PRODUCT AS AN (INTRAVENOUS (IV) PUSH OR BOLUS).**

**DO NOT COMBINE, DILUTE OR ADMINISTER IT AS AN INFUSION WITH OTHER MEDICINAL PRODUCTS.**

**Any departure from the guidance listed in this protocol, must be discussed with sponsor**

### **7.3 Dose Calculation**

#### **200 mg Fixed Dose**

- 2 vials (100 mg/4 mL)
- 8 mL total

### **7.4 Preparation of Infusion Solution**

Aseptic technique must be strictly observed throughout the preparation procedure preferably in a biologic safety cabinet or hood since no anti-microbial preservative is present in the solutions.

Equilibrate required number of pembrolizumab MK-3475 vials to room temperature

The preferred method of dose preparation is the volumetric method, gravimetric method is not permitted.

Choose a suitable infusion bag size so that the following conditions are met:

- Concentration of pembrolizumab MK-3475 is between 1 mg/mL and 10 mg/mL
- The infusion volume to bag capacity ratio should not be less than 0.3. In other words, the bag must be filled to at least 30% of its capacity.

Choose a suitable infusion bag material. The bag may be empty or it may contain normal saline. The following infusion bag materials are compatible with pembrolizumab (MK-3475):

- PVC plasticized with DEHP
- Non-PVC (polyolefin)
- EVA
- PE lined polyolefin

Contact Sponsor for materials not listed above

Calculate the volume of pembrolizumab (MK-3475) and normal saline required to prepare the infusion (admixture) bag

Volume of pembrolizumab (MK-3475) (mL) = required dose amount (mg) / 25 (mg/mL)

Volume of normal saline = total infusion volume – volume of pembrolizumab (MK-3475) from above

If a bag pre-filled with normal saline is being used, remove the excess volume of normal saline using a sterile syringe (Polypropylene, latex-free) attached to a suitable needle.

Keep in consideration the excess bag fill volume as well as the volume of pembrolizumab (MK-3475) to be added to the bag to prepare the infusion solution. This helps ensure that the concentration in the bag can be accurately calculated and falls within the acceptable range of 1 mg/mL to 10 mg/mL. If the site would like to proceed without removing excess saline they must ensure that the concentration of MK-3475 would still fall within acceptable range.

If an empty bag is being used, withdraw the necessary volume of normal saline from another appropriate bag and inject into the empty bag. Keep in consideration the volume of pembrolizumab (MK-3475) to be added to the bag to prepare the infusion solution.

Withdraw the required volume of pembrolizumab (MK-3475) from the vial(s) (up to 4 mL from each vial) using a sterile syringe attached to a suitable needle. The vial(s) may need to be inverted to remove solution.

Volume of pembrolizumab (MK-3475) (mL) = required dose amount (mg) / 25 (mg/mL)

**Note:** If it is necessary to use several vials, it is advisable to withdraw from several vials into a suitable size single use syringe using a new needle for each vial.

Add the required pembrolizumab (MK-3475) into the infusion IV bag containing normal saline and gently invert the bag 10-15 times to mix the solution.

Pembrolizumab (MK-3475) solutions may be stored at room temperature for a cumulative time of up to 4 hours. This includes room temperature storage of admixture solutions in the IV bags and the duration of infusion.

In addition, IV bags may be stored under refrigeration at 2 °C to 8 °C (36 °F to 46 °F) for up to 20 hours. If refrigerated, allow the IV bags to come to room temperature prior to use.

### **DO NOT FREEZE THE PEMBROLIZUMAB (MK-3475) INFUSION SOLUTION.**

Discard any unused portion left in the vial as the product contains no preservative

#### **7.5 Administration**

Pembrolizumab (MK-3475) infusions should be administered in 30 minutes, with a window of -5 and +10 minutes, using an infusion pump. A central catheter is not required for infusion; however if a subject has a central venous catheter in place, it is recommended that it be used for the infusion.

The following infusion set materials are compatible with (pembrolizumab) MK-3475:

- PVC Infusion set that is plasticized using DEHP
- PVC and tri-(2-ethylhexyl) trimellitate (TOTM) infusion set
- Polyethylene lined PVC infusion set
- PVC Infusion set that is plasticized using Di-2-ethylhexyl Terephthalate (DEHT)
- Polyurethane set

Contact Sponsor for materials not listed above

A sterile, non-pyrogenic, low-protein binding 0.2 to 5 µm in-line filter made of polyethersulfone (PES) must be used during administration to remove any adventitious particles. If the infusion set does not contain 0.2 to 5 µm in-line filter, it is recommended to

use 0.2 to 5  $\mu$ m add-on filter which may contain an extension line (Note: the materials of the extension line and filter should be as mentioned above).

Attach the infusion line to the pump and prime the line, either with normal saline (at least 25 mL) or with infusion solution as per local SOP, before starting the infusion.

Infuse pembrolizumab (MK-3475) over approximately 30 minutes, with a window of -5 and +10 minutes, through a peripheral line or indwelling catheter.

Ensure the entire contents of the bag are dosed and all remaining drug solution in the line is administered according to institutional guidelines for saline flushing.

Document volume administered according to data entry guidelines.

In case of infusion reactions, infusion rate may differ; refer to protocol section 8.2 for specific instructions.

Whenever possible, the lowest infusion rate should be used that will allow completion of the infusion within the 30 minutes.

Maximum rate of infusion should not exceed 6.7 mL/min. through a peripheral line or indwelling catheter. However, when it is necessary to infuse a larger volume (i.e. 250 mL), the flow rate may go as high as 10 mL/min (maximum) in order to keep the infusion within the window as defined above.

**DO NOT CO-ADMINISTER OTHER DRUGS THROUGH THE SAME INFUSION LINE.**

**UNUSED INFUSION SOLUTION FOR INJECTION SHOULD NOT BE USED FOR ANOTHER INFUSION OF THE SAME SUBJECT OR DIFFERENT SUBJECT.**

## **7.6 Accountability and Compliance**

The investigator is responsible for keeping accurate records of the clinical supplies received from Merck or designee, the amount dispensed to and returned by the subjects and the amount remaining at the conclusion of the trial.

Upon completion or termination of the study, all unused and/or partially used investigational product will be destroyed at the site per institutional policy. It is the Investigator's responsibility to arrange for disposal of all empty containers, provided that procedures for proper disposal have been established according to applicable federal, state, local and institutional guidelines and procedures, and provided that appropriate records of disposal are kept.

## **7.7 Concomitant Medications**

Medications or vaccinations specifically prohibited in the exclusion criteria are not allowed during the ongoing trial. If there is a clinical indication for one of these or other medications or vaccinations specifically prohibited during the trial, discontinuation from trial therapy or vaccination may be required. The investigator should discuss any questions regarding this with the study sponsor (principal investigator). The final decision on any supportive therapy or vaccination rests with the investigator and/or the subject's primary physician.

### **7.7.1 Acceptable Concomitant Medications**

All treatments that the investigator considers necessary for a subject's welfare may be administered at the discretion of the investigator in keeping with the community standards of medical care. All concomitant medication will be recorded on the case report form (CRF) including all prescription, over-the-counter (OTC), herbal supplements, and IV medications and fluids. If changes occur during the trial period, documentation of drug dosage, frequency, route, and date may also be included on the CRF.

All concomitant medications received within 28 days before the first dose of trial treatment and 30 days after the last dose of trial treatment should be recorded. Concomitant medications administered after 30 days after the last dose of trial treatment should be recorded for SAEs and ECIs as defined in Section 7.2.

### **7.7.2 Prohibited Concomitant Medications**

Subjects are prohibited from receiving the following therapies during the Screening and Treatment Phase (including retreatment for post-complete response relapse) of this trial:

- Antineoplastic systemic chemotherapy or biological therapy. Hormonal therapies or other long-term adjuvant therapies may be approved after discussion with the principal investigator.
- Immunotherapy not specified in this protocol
- Chemotherapy not specified in this protocol
- Investigational agents other than pembrolizumab
- Radiation therapy
  - Note: Radiation therapy to a symptomatic solitary lesion or to the brain may be allowed at the investigator's discretion.
- Live vaccines within 30 days prior to the first dose of trial treatment and while participating in the trial. Examples of live vaccines include, but are not limited to, the following: measles, mumps, rubella, varicella/zoster, yellow fever, rabies, BCG, and typhoid vaccine.
- Systemic glucocorticoids for any purpose other than to modulate symptoms from an event of clinical interest of suspected immunologic etiology. The use of physiologic doses of corticosteroids may be approved after consultation with the study sponsor (principal investigator).

Subjects who, in the assessment by the investigator, require the use of any of the aforementioned treatments for clinical management should be removed from the trial. Subjects may receive other medications that the investigator deems to be medically necessary.

The Exclusion Criteria describes other medications which are prohibited in this trial.

There are no prohibited therapies during the Post-Treatment Follow-up Phase.

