## 9 STUDY CALENDAR

**CYCLE** Calendar: 1 cycle = 21 days ( $\pm$  3 days)

Examination	Screening 	C1 	C2	C3	C4	C5	C6	C7 and beyond	End of Treatment	Follow-up 
Informed consent	X									
Medical history/baseline AE	X									
Eligibility criteria	X									
Vital signs	X	X	X	X	X	X	X	X	X	
Physical examination	X	X	X	X	X	X	X	X	X	X
ECOG performance status	X	X	X	X	X	X	X	X	X	
Hematology 	X	X	X	X	X	X	X	X	X	
Chemistry 	X	X	X	X	X	X	X	X	X	
Urinalysis	X								X	
T3, free T4, TSH 	X				X			X 		
PT, PTT, INR	X									
Pregnancy test 	X									
Review Adverse events and events of clinical interest		X	X	X	X	X	X	X	X	
Review of concomitant medications	X	X	X	X	X	X	X	X		
Archival tissue for PD-L1 analysis 	X									
Archival tissue for TMB analysis 	X									
Archival tissue for Ki-67 analysis 	X									
ECG 	X									
CT scans (c/a/p) 	X			X		X		X 	X	X 
Disease Assessment (irRECIST) 	X			X		X		X	X	X
MRI 										
Study drug 		X	X	X	X	X	X	X		

- 1 ALL Pre-study/Screening procedures should be completed within 4 weeks of study enrollment - with the exception of laboratory tests which need to be completed within 14 days prior to study enrollment.
- 2 Hematology includes CBC with differential and platelets
- 3 Chemistry includes Albumin, Alkaline Phosphatase, Aspartate Aminotransferase, Alanine Aminotransferase, Total Bilirubin, Calcium, Carbon Dioxide, Creatinine, Chloride, Glucose, Potassium, Protein, Sodium, and Urea Nitrogen
- 4 T3, free T4, TSH to be performed at screening and every 9 weeks (every third cycle) while on treatment
- 5 Pregnancy test must be done at screening and within 72 hours of starting study treatment for all women of childbearing potential and repeated as clinically indicated. Serum or urine tests may be used. If urine pregnancy is positive, confirm with serum.
- 6 If the patient consented to the optional testing and tissue is available (either from archival tissue or fresh biopsy tissue), PD-L1 analysis will be performed at central lab. If fresh tissue is being used, it should be obtained during screening window prior to study treatment. See section 15.

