- 7 If clinically indicated, and not previously performed, tumor mutation burden analysis will be performed at central lab. If performed, results should be collected for the study. See section 15.
- 8 Patients must have existing Ki-67 results from archival tissue or available tissue for Ki-67 testing. If no archival tissue is available the subject must agree to a fresh biopsy for testing to qualify for the study. Ki-67 analysis will be performed at local lab if not previously performed. See section 15.
- 9 ECG will be done if medically indicated
- 10 CT of the abdomen/chest/pelvis must be repeated every 6 weeks through C12 (36 weeks), then every 12 weeks until disease progression. Progression must be confirmed no earlier than 4 weeks and no later than 8 weeks. Scans must be completed within 7 days prior to the next dosing cycle.
- 11 Pembrolizumab 200 mg IV q3weeks
- 12 Follow-up should occur no less than every 6 months for 4 years following study enrollment
- 13 Baseline procedures do not need to be repeated if screening procedures have been done within 7 days of start of treatment
- 14 MRI may be required at baseline for subjects with previously treated brain metastases

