## 10 STUDY PROCEDURES

### 10.1 Screening Evaluations

- Informed Consent
- Physical examination with vital signs and ECOG Performance Status
- Review of medical history/baseline symptoms
- Review baseline concomitant medications
- Laboratory assessments:
  - CBC with differential
  - CMP to include sodium, potassium, chloride, carbon dioxide or bicarbonate, blood urea nitrogen (BUN), creatinine, glucose, total protein, albumin, calcium, AST, ALT, alkaline phosphatase, total bilirubin
  - Coagulation to include PT/INR and aPTT
  - Thyroid function tests to include TSH, total T3, and free T4
  - Serum or urine pregnancy test (for women of childbearing potential) within 72 hours of starting study treatment
  - Urinalysis
- 12-lead ECG if clinically indicated
- CT scans and disease assessments for baseline irRECIST
- MRI only for subjects with previously treated brain metastases
- Archival tissue or fresh tissue biopsy (if archival tissue is not available) for Ki-67 testing (see footnote #8 in calendar)
- Archival tissue or fresh biopsy for central PD-L1 analysis if patients consent to optional testing.

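### Section 7.7.2 allows radiation without protecting target lesions, and no response rule stops the resulting shrinkage from counting as irPR

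*Combined protocol and SAP*

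**What the plan says.** **The ban and its exception (7.7.2).** "Subjects are prohibited from receiving the following therapies during the Screening and Treatment Phase": the list that follows covers systemic anticancer therapy, investigational agents and radiation. The radiation item carries a note: "Radiation therapy to a symptomatic solitary lesion or to the brain may be allowed", at the investigator's discretion. The note does not mention target lesions. The paragraph after the list says that subjects who need any of the listed treatments should be taken off the trial.

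**Response rules.**
- 11.1.1 chooses up to five target lesions by size, repeatability and representativeness. It has no rule for irradiated lesions.
- irPR is a fall of at least 30% from the baseline sum of diameters, seen on two consecutive observations at least 4 weeks apart.
- 11.1.2 takes the best response up to progression, with no cut-off at other anticancer therapy.
- 11.1 and 11.3 describe evaluability by a baseline scan, a 6-week scan and two cycles of drug.

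**Timing before Day 1.**
- 5.2.6 excludes a patient who "Has had prior chemotherapy, targeted small molecule therapy, or radiation therapy within 2 weeks prior to study Day 1". 5.1.12 sets the same two weeks under "Last dose of any antineoplastic therapy".
- Section 9, footnote 1: "ALL Pre-study/Screening procedures should be completed within 4 weeks of study enrollment". The screening list in 10.1 includes "CT scans and disease assessments for baseline irRECIST".
- No sentence places that CT after the last prior therapy.

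**The concern.** The primary endpoint is irPR plus irCR in a single arm. No control group shows how much shrinkage would have occurred without pembrolizumab, so the response rules alone must separate a drug effect from another cause. A patient whose painful target lesion is irradiated under the note, and who has not progressed, can remain on study and evaluable. Shrinkage of that lesion is then measured against the pre-radiation baseline. Confirmation four or more weeks later does not help, because a lasting radiation effect would also be confirmed.

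The counts that decide the trial are small, so one such response can change the outcome. Without a written rule, the choice would be made case by case in an open-label trial.

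**Working it through.** **1. The plan's design.** Inputs from Section 12: null rate 10%, alternative 25%, stop at 0–1 of 13, reject at 6 or more of 34.

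P(reject | p) = Σ over x = 2…13 of P[Bin(13, p) = x] × P[Bin(21, p) ≥ 6 − x]

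This gives 0.0957 at p = 0.10 and 0.8108 at p = 0.25. A search over two-stage designs with alpha ≤ 0.10 and power ≥ 0.80 returns the same design as optimal, with expected sample size 20.95 under the null. The design figures are correct and are not in question.

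**2. When radiation alone can produce irPR.** I use the sum of diameters, as the response categories do, although 11.1.1 also speaks of a sum of products. Suppose the other target lesions do not change, no new lesion appears and non-target disease does not progress. The irradiated lesion must then carry this share of the baseline sum:

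share = 0.30 / proportional shrinkage of that lesion

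| Shrinkage of the irradiated lesion | Share of baseline sum needed |
|---|---|
| 100% | 30% |
| 50% | 60% |
| 30% | 100% (sole target lesion) |

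With lesions of equal size, losing one is enough with one, two or three target lesions (1/3 = 33%), but not with four (25%) or five (20%). The risk lies with patients who have few target lesions or one dominant one.

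**3. Effect of one misattributed response.** One patient is certain to be scored as a responder and the other 33 respond at 10%.
- In stage 2: Σ over x ≥ 2 of P[Bin(13, 0.10) = x] × P[Bin(20, 0.10) ≥ 5 − x] = 0.1705
- In stage 1: Σ over x ≥ 1 of P[Bin(12, 0.10) = x] × P[Bin(21, 0.10) ≥ 5 − x] = 0.2156

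**4. Effect averaged over how often it happens (assumed).** Let f be the share of patients affected, and q the chance that the other therapy alone gives a confirmed response. Neither is in the documents. The effective null rate is 0.10 + 0.90 × f × q.

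| f | q | Effective rate | P(reject) |
|---|---|---|---|
| 2% | 5% | 0.1009 | 0.099 |
| 5% | 5% | 0.10225 | 0.104 |
| 5% | 10% | 0.1045 | 0.112 |
| 10% | 10% | 0.109 | 0.130 |
| 10% | 20% | 0.118 | 0.169 |

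**5. The baseline CT.** Taking registration as enrollment, the CT may be 28 days before it, and Section 13 asks for treatment within 5 days after it. Washout ends 14 days before Day 1. Footnote 1 and the washout criteria alone therefore leave 28 − 14 = 14 days, or 28 + 5 − 14 = 19 days, in which therapy could follow the CT. The ban in 7.7.2 narrows this, as discussed under the objection.

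**The case against.** **The removal sentence.** The strongest reply is that 7.7.2 itself sends patients who need a listed treatment off the trial. For patients who stop without progression, 7.8 ends disease-status follow-up at a non-study cancer treatment. If removal applied, later shrinkage would not normally be assessed. A reader might otherwise infer that the plan gives clean, unopposed permission for on-treatment radiation; it does not. But the note expressly allows this radiation, the general sentence does not say that it overrides the note, and neither says how a response should be scored. What stands is a conflict that leaves the gap open.

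**The baseline CT.** A reader might infer that chemotherapy given between the baseline CT and Day 1 can be credited to pembrolizumab. The documents do not support that for a CT done as a study procedure. Section 13 puts such procedures after consent, and 7.7.2 on its natural reading bars systemic therapy during screening. Superscript 10 is also attached to the CT rows, so "Scans must be completed within 7 days prior to the next dosing cycle" may cover the screening CT. If it does, no permitted therapy fits between that CT and Day 1. If it does not, two cases remain: a standard-of-care CT taken before consent and used as baseline, which the documents neither mention nor authorise, and radiation under the note given after the CT but before the washout limit. The bias is not all one way either: growth between an old CT and Day 1 works against irPR.

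**Other safeguards.** Under 5.2.12 the investigator can exclude a patient for "any condition, therapy, or laboratory abnormality that might confound the results of the trial", but that is discretionary and applies at entry. The evaluability wording begins with *generally*, so it need not be exhaustive. The response criteria come from a cited publication, so I can speak only for the protocol's account of them.

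**Size.** The figures 0.171 and 0.216 assume that a false response has occurred; a misread scan would have the same effect. They show how sensitive the design is, not how often the note would be used. That is correct, and it limits the weight of the point.

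**Conclusion.** The point holds for radiation to a target lesion after the baseline CT. Followed as written, the plan can score radiation shrinkage as irPR, and its two statements on whether the patient stays on trial conflict. irCR is a remote possibility, because all non-nodal target lesions and all non-target lesions would have to disappear.

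The frequency is unknown and probably low. The event needs discretionary radiation, a symptomatic solitary lesion that is also a target, a large share of the baseline sum, no earlier progression and later confirmation. A reader might infer from step 3 that the trial's type I error is really 0.17 to 0.22. It is not: those values are conditional on one false response. Over the assumed range in step 4 the error runs from 0.099, almost unchanged, to 0.169.

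This is a worthwhile improvement at very low cost. The sample size and decision rule are unaffected. The baseline CT needs a clarification only.

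**What to change.** **7.7.2.** State that the removal sentence does not apply to radiation permitted by the note, and that such radiation should go to a non-target lesion where clinically possible.

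**11.1.1 and 11.1.2.** Add:

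> If a target lesion is irradiated after the baseline CT, the patient stays evaluable. irPR or irCR confirmed before the radiation stands; no irPR or irCR is first credited after it, and the patient is otherwise counted as a non-responder. Growth of any lesion, including the irradiated one, and new lesions still count toward irPD.

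**Do not drop the irradiated lesion from the sums.** That can hide growth and create a response. Take target lesions of 40, 30 and 30 mm. The first grows to 60 mm and is irradiated without shrinking; the others fall to 20 mm each. The full sum goes from 100 to 100 (irSD). With the first lesion removed it goes from 60 to 40, a 33% fall, which would be irPR if confirmed.

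**Section 9, footnote 1 (clarification).** If radiation or systemic anticancer therapy is given after the baseline CT and before Day 1, repeat the CT before the first dose. Exempt the ongoing hormone therapy allowed by 5.1.12 and 5.2.6.

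**Cost.** A few sentences in the next amendment, an occasional repeat CT and no extra patients. The downside is that a true drug response first seen after radiation is not counted. With one patient certain not to count and the other 33 responding at 25%, power falls from 0.811 to 0.774 (stage 1) or 0.798 (stage 2). At 10%, type I error falls from 0.096 to 0.082 or 0.087.
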